4.2 INCLUSION AND EXCLUSION CRITERIA

Patient Inclusion Criteria	Patient Exclusion Criteria
Age ≥ 60 years	Previous study participation
English speaking	Active enrollment in or discharge to hospice
Dane County, WI or Monroe County, NY resident	Homelessness
UW or UR affiliated PCP	Behavioral health treatment as primary reason for ED visit
Independent home dwelling (no prisoners, nursing home, assisted living)	Participation in a transition care team program or intensive care management patient
Discharge home from the ED	ESI 1 patient (highest acuity, assigned by ED staff)
Have a working telephone	Unable to obtain consent from patient or proxy

Caregiver Inclusion Criteria	Caregiver Exclusion Criteria
Age ≥ 18 years	Unable to obtain consent / no decisional capacity
English speaking	
Able to understand and complete informed	

consent	
Have a working telephone	

4.3 DISCUSSION OF SUBJECT POPULATION

We have chosen this subject population because the existing literature has indicated that this is the group that is of greatest risk after being discharged from the ED. We have limited the population as per the exclusion criteria to: 1) maximize study rigor; 2) eliminate conflict with existing programs; 3) protect patient autonomy and safety. We are enrolling only English-speaking subjects because, based on our previous studies, it is rare for older adult ED patients at these two EDs to not speak English and no individual group (e.g., Spanish-speaking) requires translators with great frequency. We considered excluding patients who could not fully participate in the ED CTI due to barriers such as sensory limitations or impaired cognition. However, with our goal to maximize external validity and understand factors that lead to repeat ED visits in patients receiving the CTI, we have elected to retain these patients and account for them in our analysis. We are excluding ESI 1 patients for multiple reasons: 1) these patients have high acuity conditions and often are receiving life-saving interventions; 2) these patients are rarely discharged home; 3) these patients are rarely able to provide informed consent for a study such as this. Thus, we have elected to exclude them rather than unnecessarily expend time and effort to assess them, approach the care team, and approach the patient.

5. SUBJECT IDENTIFICATION, RECRUITMENT AND CONSENT

5.1 METHOD OF SUBJECT IDENTIFICATION AND RECRUITMENT

All study procedures will be standardized at both sites. Subjects will be identified and recruited using processes based on published best practices refined by our team.^{70,71} Following the inclusion criteria, we will recruit subjects each day in the ED at UW Hospital and Clinics and UR Medical Center-Strong Memorial Hospital and UR Medical Center-Highland Hospital. To ensure variability in the time of day at which patients present, a random time table will be created and recruiting will start at that time, and continue until a subject is enrolled.

Recruitment Model: An Emergency Department Research Associate (RA), who is a staff person employed by the Department of Emergency Medicine, will monitor the HealthLink /eRecord trackboard for eligible patients. These staff members have a broader role in the ED. They (RAs) complete duties as assigned by the Department Chair as it relates to the overall mission of the Department of Emergency Medicine (e.g., research, clinical operations such as quality improvement, communication, & process monitoring, etc.). These RAs under the direction of the ED clinical providers will approach subjects for study recruitment purposes as described below.

When a potentially eligible patient is identified, the RA will ask the primary clinical team as to whether they anticipate the patient being discharged home. If the clinical team indicates that the patient will likely be discharged home, the RA will then approach the patient and their family / informal caregivers to confirm eligibility and explain the study.

All participating patient subjects, regardless of assignment to intervention or control group, will be asked to complete three research surveys. The first survey will be completed in the privacy of their ED room and will take about 15 minutes to complete. The other two surveys will be completed over the telephone at approximately day 4 and day 30 at a time that is convenient for the subject. These survey follow-up calls will take about 10 minutes to complete and assess outcome measures. All questions are voluntary. Subjects are free to refuse to answer any survey questions they are uncomfortable with.

Patient subjects randomized to the intervention arm (CTI program) must agree to one paramedic coach home visit and up to 3 follow up phone calls to deliver CTI program clinical care over 30 days. The paramedic coach home visit will ideally occur within 24 hours of ED discharge and take approximately 1 hour. This home visit will be scheduled at a time that is convenient for the subject. During the home visit the paramedic coach will review the subject's medications, educate on red flags and emphasize provider follow-up. The phone calls will reinforce the coaching information. These interactions are organized around the validated and nationally implemented CTI program.

In the event a participating subject is admitted to the hospital directly from the initial ED visit (i.e., the primary team changes its mind based on developing results), then the subject (and caregiver where applicable) will be removed from the study because they no longer meet study eligibility criteria.

Caregiver subjects will be asked to complete an ED survey and one follow up research survey by phone at approximately day 30. The ED survey will take approximately 15 minutes to complete, and the call will take approximately 10 minutes to complete and will assess outcome measures. All questions will be voluntary.

Randomization: Randomization will occur at the site-level and occur after the treatment team has indicated that the patient will be likely discharged home, and the subject or legally authorized representative (LAR) has consented to participate on the study and the baseline survey has been completed. At that point, the subject will be randomized. This will be a stratified randomization, based upon whether or not an informal caregiver provides significant support for the patient.

In the infrequent event that the patient is admitted after consenting for the study and being randomized (but before being discharged and leaving the ED), the patient subject (and caregiver where applicable) will be withdrawn from study as an investigator initiated withdrawal because the subject no longer meets eligibility criteria (i.e hospital admission).

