After completing informed consent, the patient (and caregiver when applicable) will be asked to complete the baseline survey. When the baseline survey is complete, the patient will be informed of their randomization. If the patient is randomized to the control group, the RA will schedule the 1st follow-up call at a convenient time for the patient. If the patient is randomized to the intervention group, the RA will ask the patient for a convenient time, within the next 24 hours, for the paramedic coach to make the home visit. The RA will schedule the visit and give the patient a reminder card with a photo of the coach and the time the home visit is scheduled. For those patient subjects who lack capacity, the LAR (surrogate) will be required to attend the paramedic coach home visit.

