7. SUBJECT WITHDRAWALS

All subjects will be advised in the written informed consent forms that they have the right to withdraw from the study at any time without prejudice. Withdrawal will only occur if the subject indicates that he / she no longer wishes to participate. For subjects who withdraw from the study, we will clarify the level of withdrawal. For those who wish their records to be fully expunged from the study, we will destroy all information except for the consent form, but add a note indicating the date and time of withdrawal. For those who wish to cease participating in the CTI program and follow up activities, we will request permission to retain them in the study and continue medical record review until the end of study chart review.

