12.2 PLANNED STATISTICAL ANALYSIS

Through the analytic methods used in Aims 2 and 3, we will assess differences between groups related to process outcome measures (Aim 2) and will assess the effectiveness and cost-effectiveness of the ED-to-home CTI (Aim 3). In Aim 4, we will identify predictors of repeat ED use among intervention group subjects. We will characterize of our study sample using descriptive statistics and corresponding measures of variation. We will assess for differences between groups at baseline despite randomization in key characteristics (e.g., demographics, comorbidities) using t-tests for continuous variables and Chi-square tests for categorical variables, using Fisher's exact test where appropriate. These comparisons will enable the identification of covariates to be controlled in our multivariable analyses. If distributional assumptions associated with a particular statistical procedure are violated, we will use appropriate transformations or non-parametric alternatives. Primary analyses will be performed under the intent-to-treat principle, keeping subjects in the group to which they were originally randomized, regardless of compliance or adherence to study procedures. We will conduct sensitivity analyses among subjects who complete all study procedures to evaluate the effect of the intervention among those who complete all study-related procedures. Hypothesis-driven comparisons will be made to control the family-wise type I error rate at 0.05 (two-sided) for the primary hypothesis.

Caregiver Subject Analysis: Although not an original aim of the study, we have obtained permission from the NIH and will perform a limited analysis of caregiver activation. This was only recently added to

the CTI. To compare the caregiver activation between the control and intervention groups, we will administer the FCAT. The FCAT will be scored as 1-6 points per question, for a score ranging from 10-60. We assume that 30% of participants will have caregivers with them, the average score will be 30, and we will look for a 5 point difference. Our sample size will allow a power of >0.8 for a t-test ($\alpha=0.05$).

Hyp 1A: More program participants will demonstrate understanding of their ED discharge instructions, red flags that indicate a worsening of their condition, and how to respond to the red flags three days after ED discharge.

Hyp 1B: More program participants will implement medication changes made in the ED within three days of ED discharge.

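### Withdrawing randomised patients who are admitted before leaving the ED conflicts with the plan's intent-to-treat and withdrawal rules, and could bias the primary comparison, probably slightly.

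*Combined protocol and SAP*

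**What the plan says.** Section 5.1 (Randomization) has randomisation "occur after the treatment team has indicated that the patient will be likely discharged home", after consent and the baseline survey. Eligibility at that point is therefore a forecast.

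Section 5.2 describes the next step: "When the baseline survey is complete, the patient will be informed of their randomization". For a patient allocated to the Care Transitions Intervention (CTI), the research associate (RA) books the home visit and will "give the patient a reminder card with a photo of the coach and the time the home visit is scheduled". All of this happens in the ED.

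Section 5.1 deals twice with patients who are then admitted. One paragraph says that they "will be removed from the study because they no longer meet study eligibility criteria". The other begins "In the infrequent event that the patient is admitted after consenting for the study and being randomized" and says that the patient is "withdrawn from study as an investigator initiated withdrawal because the subject no longer meets eligibility criteria".

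Two other sections point the other way. Section 12.2 makes the primary analysis intent-to-treat, "keeping subjects in the group to which they were originally randomized, regardless of compliance or adherence to study procedures", and states no exception. Section 7 says "Withdrawal will only occur if the subject indicates that he / she no longer wishes to participate".

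**The concern.** The removal trigger, admission rather than discharge, occurs after randomisation and after the allocation is known to the patient and the RA. If the admission decision can respond to the allocation, a rule worded identically for both arms can still remove different patients from each. A clinician might, for example, send a borderline patient home more readily knowing that a paramedic will call within a day or two. The CTI arm would then keep more high-risk patients and the effect would be diluted. If the CTI arm lost more high-risk patients, a benefit could appear where there is none.

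There is also a problem that needs no assumption about behaviour. Following section 5.1 leaves randomised patients out, while section 12.2 calls the result intent-to-treat. No section provides for outcome follow-up of these patients, for reporting them by arm, or for an analysis that restores them. The missing-data text in section 12.2 does not mention them. The continued record review in sections 3.2 and 7 is for subjects who ask to stop contact or participation.

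**Working it through.** **Setting the sections side by side.** Section 5.1 removes some randomised patients at the investigator's initiative. Section 7 permits withdrawal only at the subject's initiative. Section 12.2 keeps everyone as randomised. The three cannot all be followed for a patient admitted after randomisation.

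**Inputs from section 12.1.** Control risk 20%, CTI risk 15%, two-sided 5% level, 80% power, 860 per group needed, 25% attrition, 1200 per group recruited. The standard two-proportion formula gives 906 per group, not 860, and power at 860 is 77.9%. That is a separate matter. I use 1200 × 0.75 = 900 analysed per arm, where

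power = Φ{[|p1 − p2|√n − 1.96√(2p̄(1 − p̄))] / √(p1(1 − p1) + p2(1 − p2))} = Φ{(1.5 − 1.053)/0.536} = 79.8%.

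**Assumed inputs.** The plan gives no admission rate beyond calling the event infrequent, and no revisit risk for those admitted. I assume removal of 1% vs 2% or 2% vs 4%, and a revisit risk r of 30%, 40% or 60% in those removed.

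**Equal removal, unrelated to arm.** The bias is zero and only size is lost. At 1% removed, 1200 × 0.99 × 0.75 = 891 per arm and power is 79.4%. At 2%, 882 per arm and 79.0%.

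**Unequal removal, no true effect.** With 20% risk in all randomised patients and a share *a* of an arm removed, the risk in those analysed is (0.20 − a·r)/(1 − a). For 2% vs 4% at r = 60%: (0.20 − 0.012)/0.98 = 19.18% and (0.20 − 0.024)/0.96 = 18.33%, a spurious difference of 0.85 points. The standard error is √(2 × 0.20 × 0.80/900) = 0.0189, so the shift is 0.0085/0.0189 = 0.45 standard errors.

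The last two columns give the consequence in each direction. Type I error applies if there is no true effect. Power applies if the bias dilutes a true 20% vs 15%; it is approximated by adding the spurious difference to 15% in the power formula.

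| Removed | r | Spurious difference (points) | Type I error | Power if diluted |
|---|---|---|---|---|
| 1% vs 2% | 30% | 0.10 | 5.0% | 78.0% |
| 1% vs 2% | 40% | 0.21 | 5.1% | 76.2% |
| 1% vs 2% | 60% | 0.41 | 5.6% | 72.3% |
| 2% vs 4% | 30% | 0.21 | 5.2% | 76.1% |
| 2% vs 4% | 40% | 0.43 | 5.6% | 72.0% |
| 2% vs 4% | 60% | 0.85 | 7.4% | 63.1% |

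If those removed have the same 20% risk as everyone else, the bias is zero even when removal is unequal.

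**The case against.** The strongest reply is that the mechanism is assumed. Section 5.2 tells the patient and involves the RA; no section says that the treating team learns the arm. Section 5.1 gives developing results as the reason for a change of plan. Section 9.2 says that primary ED care is complete before consent and that research staff work independently of the ED physician. Appendix A, section 1.1, says that discharge cannot be determined until critical care is finished. The event is called infrequent. It can also be argued that these patients never met the eligibility criterion, that they had received no coaching, and that leaving the study is not expressly leaving the analysis set. Finally, 900 per arm is pessimistic, because ED use also comes from records. If records recovered all 1200 per arm, power without bias would be 90%.

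Most of this limits the size, and I accept it as such. It does not remove the point:

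- No section keeps the allocation from the ED team. Section 6.3 describes only the survey staff as blinded, and section 5.1 has RAs approaching patients under the direction of ED clinicians.
- Section 5.1 itself provides for admission after randomisation, so care is not always settled by then.
- Ineligibility that arises after randomisation is not a baseline error that can be corrected without regard to arm.
- Exclusion from analysis is the natural reading of removal. If it is not meant, the plan should say so.
- More analysed patients raise power but do not shrink the bias.

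A reader might infer that the primary result will be biased, or that power could fall to about 60%. The documents do not support either. A fall to 60% needs a bias of 1.0 point, for example a 5-point between-arm gap in retained borderline patients whose revisit risk is 40%. A gap that wide fits poorly with an infrequent event. Nor do the documents fix the direction: dilution is one plausible outcome, not the only one.

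**Conclusion.** The inconsistency is established from the text: section 5.1 cannot be followed together with sections 7 and 12.2, and following it gives an analysis that is not intent-to-treat as the plan defines it. The bias is possible, not shown, and probably small. It requires both that removal differs by arm and that those removed differ in revisit risk from the rest. Under the assumed scenarios it lies between about 0.1 and 0.9 points, in either direction, against a 5-point target; without dependence on arm it is zero. The documents give neither the admission rate nor the risk of those admitted, so these figures illustrate the range and do not estimate it. The change is worth making because the remedy is simple, not because the primary result is shown to be unsafe.

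**What to change.** 1. Keep consent and the baseline survey where they are, but generate and reveal the allocation only once the ED discharge decision is entered. This removes nearly all of the problem at source.
2. For any patient still admitted after randomisation, replace the investigator-initiated withdrawal with retention in the intent-to-treat set, using ED use over 30 days from records. The endpoint then needs a defined time origin, for example randomisation, because counting 30 days from ED discharge has no clear start for someone admitted from the index visit.
3. If the sponsor prefers to keep the exclusion, call the set a modified intent-to-treat set, report removals by arm, and add a sensitivity analysis of all randomised patients.
4. Reconcile sections 5.1, 7 and 12.2 so that they state one rule.

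The cost is one changed step in the RA's workflow, plus wording. The RA has to wait for the discharge decision, and booking the coach visit and handing over the card move into the departure window. Section 6.1 wants that window kept short, so the step should be as brief as possible. Retaining admitted patients also means record review for a few more subjects.

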5.2 PROCESS OF CONSENT

For consent, we have developed an approach (in conjunction with the UR IRB) to minimize coercion and undue influence. Consent will only be performed by individuals who are listed on the IRB application and who are IRB approved and authorized to obtain consent. The process has been established to provide enough information to allow a thoughtful decision and ensure enough time to allow a considered decision. Because this study includes vulnerable subjects (older patients, patients with potentially diminished capacity), previously implemented processes are being used. We estimate that less than 2% of the participating subjects will lack decisional capacity (~10% of older adult ED patients lack decisional capacity, and the vast majority are admitted to the hospital, thus excluded from this study), but have built mechanisms to ensure they are identified.

Process:

All study procedures will be standardized at both sites. After a potentially eligible patient (and caregiver where applicable) is identified, the RA will ask the primary clinical team whether they anticipate the patient being discharged home. If the clinical team indicates that the patient will likely be discharged home, the RA will then approach the patient and their family / informal caregivers to confirm eligibility. In the privacy of the subjects' ED room the RA will explain the study, its benefits and the potential risks of participation. The ED patient will then be given the combined consent and HIPAA authorization form and allowed as much time as they need to read it and ask questions. If the patient agrees to participate, decisional capacity will be evaluated by the RA to ensure that participants understand the risk and benefits of the study before obtaining informed consent. The decisional capacity evaluation used has previously been approved by the UR IRB. It assesses the potential subject's understanding of the study. This process is more conservative than the UW IRB policy "Research with Adult Participants Lacking

Capacity to Consent” (Section II). The patient will be involved in the consent process as much as possible and will be asked to provide assent by the researchers. The subject's assent will be required and will be documented on the consent form. This documentation will be retained in the subject's research record. Surrogates (LAR) will be informed that their decisions should be based upon what the surrogate believes is consistent with the subjects wishes if they possessed capacity, and if a subject's wishes cannot be determined, surrogate decisions should be based upon what the surrogate believes to be in the subject's best interest.

If the patient lacks decisional capacity, the RA will discuss the study further with a LAR present in the ED. If no LAR is present, then the subject will not be included in the study. Priority of decision makers is as follows: 1) research power of attorney, if present; 2) court appointed guardian; 3) power of attorney for healthcare; 4) next of kin in the following order: spouse or registered domestic partner, adult child, parent, adult sibling, grandparent, adult grandchild, or close friend. If the LAR agrees to study participation, the study coordinator will confirm decisional capacity of the LAR and then ask the LAR to sign the combined consent and HIPAA authorization form. If the LAR lacks decisional capacity, then the subject will not be included in the study. The patient and the LAR will be given a copy of the signed consent forms.

Informed consent will be obtained from caregivers present in the ED. Caregivers will be assessed for decisional capacity using the same methods as with the patient subject. Caregivers without decisional capacity will not be eligible to join study.

In cases where the capacity of the subject is in doubt, the RA will consult with an ED physician or clinician investigator.

[figure not shown]
After completing informed consent, the patient (and caregiver when applicable) will be asked to complete the baseline survey. When the baseline survey is complete, the patient will be informed of their randomization. If the patient is randomized to the control group, the RA will schedule the 1st follow-up call at a convenient time for the patient. If the patient is randomized to the intervention group, the RA will ask the patient for a convenient time, within the next 24 hours, for the paramedic coach to make the home visit. The RA will schedule the visit and give the patient a reminder card with a photo of the coach and the time the home visit is scheduled. For those patient subjects who lack capacity, the LAR (surrogate) will be required to attend the paramedic coach home visit.

